9.4. Rationale for Selection of Doses in the Study

Protocol IBHD dosing transition to U-500R MDI and titration regimens for the CSII and MDI treatment groups are guided by initial insulin TDD (based on the highest TDD recorded in the 3 days before Visit 4), screening HbA1c (Visit 1), subsequent glucose monitoring, literature expert reviews (Lane 2006; Lane et al. 2009; Hirsch 2010, Lane et al. 2010; Segal et al. 2010; Reutrakul et al. 2012), efficacy and safety results from one Phase 4 clinical study (B5K-US-IBHC [Hood et al, 2015]), results from simulations performed using a systems physiology model of diabetes (Entelos PhysioLab® Modeler) based on data from previous pharmacodynamics/pharmacokinetics studies (de la Peña et al. 2011) of U-500R and U-100 Humulin regular insulin) and on expert protocol consultant advice.

Fasting and bolus for CSII and MDI therapy plasma-equivalent glucose target ranges are 80 to 140 mg/dL. Recommended administration of U-500R bolus doses, within approximately

30 minutes before meals by CSII or MDI dosing, is based on label advice and recent pharmacodynamics/pharmacokinetics study results in obese, healthy subjects that demonstrate both prandial and basal activity of U-500R (de la Peña et al. 2011). Administration of U-500R bolus doses 15 minutes before meals will be assessed in a subset of subjects participating in the continuous glucose monitoring (CGM) addendum to demonstrate glycemic impact. If the shorter bolus time period is found to be equally efficacious, there may be a potential benefit on adherence.

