### 5.11. Exploratory Efficacy Analysis

As mentioned in Section 5.2, exploratory objectives will be analyzed for Group A+B. Summary statistics for both actual values and CFBL values will be reported for each treatment by visit for the following parameters related to 7-point SMBG:

- within-day glucose variability measured by the SD of 7-point SMBG
- between-day glucose variability measured by the SD of the SMBG during the 2-nonconsecutive-day measurement within the same scheduled visit
- within-day and between-day glucose coefficient of variation (CV) of 7-point SMBG (Clarke and Kovatchev 2009)
- average daily risk range (ADRR) defined by (Kovatchev et al. 2006)

- mean of daily differences (MODD) calculated as the average of the difference between values on different days within the same scheduled visit but at the same time

Each of the parameters above will be analyzed using an MMRM model which includes the following fixed effects: treatment (U-500R CSII, U-500R MDI), weeks on treatment, the interaction between treatment and weeks, and the stratification factors (U-500R at entry versus other insulins, entry HbA1c  $\geq 8.5\%$  or  $< 8.5\%$ , and nonusers versus users of GLP-1 receptor agonists or SGLT2 inhibitors). The model will also include the corresponding baseline of the response variable. An ANCOVA will also be used to compare treatment arms at endpoint using the LOCF method. The ANCOVA model will include the same fixed effects in the MMRM model but without the terms involving weeks

The postprandial contribution to total hyperglycemia will be further explored (Riddle et al. 2011). The daily blood glucose (BG) response to meals will be estimated by calculating the incremental AUC of daytime BG from the overall glucose profile. Four areas were calculated geometrically from the seven-point curve as follows:

- 1) normal glycemic exposure ( $AUC_N$ ):  $100 \text{ mg/dL} \times 24 \text{ h} = 2,400 \text{ mg/dL per hour of exposure}$
- 2) basal hyperglycemia (BHG) ( $AUC_B$ ): the area between  $100 \text{ mg/dL}$  and a line projected rightward for 24 hours from the fasting (before breakfast) glucose value in the profile (the area is taken to represent the daily abnormal glycemic exposure resulting from BHG)

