- 3) postprandial hyperglycemia (PPHG) ( $AUC_P$ ): the area above the line projected rightward from the fasting sample before breakfast and below the line connecting the 6 remaining points, minus any area below the line projected from the basal value, if applicable (this area is considered a reflection of the postprandial glycemic responses to breakfast, lunch, and dinner)
- 4) total glucose ( $AUC_G$ ): the total area under the glucose curve is the sum of the other 3 areas [ $AUC_G = AUC_N + AUC_B + AUC_P$ ]. As a result, the relative contributions of postprandial and fasting BG to the total BG increment were calculated, respectively, by using the following equations: [ $AUC_P / (AUC_B + AUC_P)$ ] x 100% for the postprandial contribution and [ $AUC_B / (AUC_B + AUC_P)$ ] x 100% for the basal contribution. Negative values were set to zero.

Analyses include Mean (SD) of and Pearson correlation (p-value) between HbA1c CFBL at Week 26 (LOCF) and each of CFBL of:  $AUC_B$ ,  $AUC_P$ ,  $AUC_G$ , BHG contribution and PPHG contribution at Week 26 (LOCF). The  $AUC_B$  and  $AUC_P$  will be analyzed separately by fitting ANCOVA model with baseline corresponding parameter as a covariate, treatment as fixed effect to compare the treatment effect.

Total hyperglycemia (%) separated by BHG and PPHG will be plotted for each treatment in bar chart format with x-axis for different HbA1c category ( $< 6.5\%$ ,  $6.5\%$  to  $< 7\%$ ,  $7\%$  to  $< 7.5\%$ ,  $7.5\%$  to  $< 8\%$ ,  $\geq 8\%$ , and overall).

Proportions of subjects with HbA1c  $\geq 9\%$  or  $< 9\%$  at Week 26 will be reported and will be analyzed using the same logistic regression model used in the analysis of the proportions of subjects achieving different HbA1c targets in Section 5.10.

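### SAP 5.11's glucose-area decomposition either fails to add up or gives impossible shares when a component is negative, notably when fasting SMBG is below 100 mg/dL, inside the trial's target range

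*SAP*

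**What the plan says.** SAP 5.11 addresses the exploratory objective on postprandial contributions to glycemic burden (Protocol 6.3, SAP 4.3), in Group A+B. It defines four areas from the 7-point SMBG profile:

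- AUC_N, normal exposure: 100 mg/dL over 24 h.
- AUC_B, basal hyperglycemia: the area between 100 mg/dL and "a line projected rightward for 24 hours from the fasting (before breakfast) glucose value in the profile".
- AUC_P, postprandial hyperglycemia: "the area above the line projected rightward from the fasting sample before breakfast and below the line connecting the 6 remaining points". Wherever the curve drops under the fasting line, that part is subtracted.
- AUC_G, total glucose: "the total area under the glucose curve is the sum of the other 3 areas".

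The postprandial and basal shares are AUC_P and AUC_B, each divided by (AUC_B + AUC_P). The only provision for low values follows the share equations: "Negative values were set to zero". It does not say which values.

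The SAP reports means (SD) and correlates the change in HbA1c with the change in AUC_B, AUC_P, AUC_G and both shares. It compares AUC_B and AUC_P between arms by ANCOVA, and plots the basal and postprandial split by HbA1c category.

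Protocol 9.4 states: "Fasting and bolus for CSII and MDI therapy plasma-equivalent glucose target ranges are 80 to 140 mg/dL". The titration tables in Protocol 9.8 make no dose change for a median within that band.

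**The concern.** The normal line is fixed at 100 mg/dL, but AUC_P is measured from the subject's own fasting value F. For F of 100 or more, with AUC_P not negative, the three pieces fit together. For F below 100, AUC_B as a signed area is negative, and the result depends on what the zeroing rule acts on. A negative AUC_P, where glucose runs mostly below the fasting value, raises the same question.

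A fasting value of 80 to 99 mg/dL is one that the protocol treats as on target, so this is not a freak case. At stake are the reported AUC_G values, the two shares and their correlations with HbA1c change. A share with a small or negative denominator can dominate a mean or a Pearson correlation.

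**Working it through.** **Inputs.** The definitions and the 80 to 140 mg/dL range are from the documents. The profiles are illustrative. Assumed clock times are 0700, 0900, 1200, 1400, 1800, 2000 and 0300, with the curve closed at the fasting value at 24 h. The SAP does not say how to close the curve after 0300.

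**The plan's own figure.** AUC_N = 100 × 24 = 2,400 mg·h/dL, as stated.

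**Algebra.** Let T be the trapezoid area over 24 h. With signed areas, AUC_B = 24 × (F − 100) and AUC_P = T − 24F. Then AUC_N + AUC_B + AUC_P = 2,400 + 24F − 2,400 + T − 24F = T, so the signed sum is exact. Setting a negative component to zero raises the sum by the size of that component. If only AUC_B is negative, the excess is 24 × (100 − F), whatever the shape of the profile.

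**Profile 1: F = 80, rises over fasting of 70, 30, 70, 30, 70 and 15.**

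- AUC_P = 70 + 150 + 100 + 200 + 100 + 297.5 + 30 = 947.5
- T = 24 × 80 + 947.5 = 2,867.5
- AUC_B = 24 × (80 − 100) = −480

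| Reading of the zero rule | AUC_G | Postprandial share |
|---|---|---|
| Areas zeroed | 2,400 + 0 + 947.5 = 3,347.5 (excess 480, +17%) | 947.5 / 947.5 = 100% |
| Only percentages zeroed | 2,400 − 480 + 947.5 = 2,867.5 (exact) | 947.5 / 467.5 = 203% |
| AUC_B as an unsigned area | 2,400 + 480 + 947.5 = 3,827.5 (excess 960) | 947.5 / 1,427.5 = 66% |

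**Profile 2 (shallow): 85/100/90/100/90/100/85.**

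- AUC_B = 24 × (−15) = −360; AUC_P = 177.5; denominator = −182.5
- Signed shares: 177.5 / −182.5 = −97% postprandial (then set to 0) and −360 / −182.5 = 197% basal. A subject with no basal hyperglycemia is reported as entirely basal.
- Areas zeroed: AUC_G = 2,400 + 0 + 177.5 = 2,577.5, against T = 2,040 + 177.5 = 2,217.5. The excess is 360.

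**Profile 3 (negative AUC_P): 150/160/120/150/115/150/130.**

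- AUC_B = 24 × 50 = 1,200; AUC_P = −265; denominator = 935
- Signed shares: −28% postprandial and 128% basal
- Areas zeroed: AUC_G = 2,400 + 1,200 + 0 = 3,600, against T = 3,600 − 265 = 3,335

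**Does AUC_P depend on the fasting level?** With the rises of Profile 1, AUC_P is 947.5 at F = 80 and at F = 120. Equal meal rises give equal AUC_P.

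**How often?** The documents give no mean or SD for fasting SMBG. If F is taken as normal, with an assumed mean of 110 to 150 and SD of 20 to 40 mg/dL, the proportion below 100 runs from 0.6% (mean 150, SD 20) to 40% (mean 110, SD 40). The average excess in AUC_G with zeroed areas, 24 × E[max(0, 100 − F)], runs from 1 to 275 mg·h/dL over the same range.

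**The case against.** The best defense is that this is one ambiguous sentence in an exploratory derivation, outside the H1 to H10 testing scheme. Each main reading gets half right: zeroed areas give a 100% postprandial share at F = 80, which is sensible, and signed areas give an exact AUC_G. The decomposition follows a cited publication, which may define the rule's scope; that cannot be checked here. If the two-day SMBG averaging in SAP 5.10 also applies to these profiles, values of F below 100 become rarer. All of this bears on importance. It does not remove the inconsistency, because no single reading gives both a correct total and usable shares.

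A reader might go further and infer that postprandial exposure is overstated, more so in the arm with lower fasting glucose, so that CSII looks worse after meals. The documents do not support that. AUC_P is defined as a net rise over fasting and does not move with F, so the ANCOVA on it shows no spurious arm difference when meal rises are equal. That CSII lowers fasting glucose more is a hypothesis (H2, H7), and those concern laboratory FPG. Nor is the postprandial share always too high: it is 203%, 100% or 66% for Profile 1, depending on the reading, and −97% for Profile 2.

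It is also tempting to measure AUC_P from the larger of F and 100. That would give 467.5 instead of 947.5 at F = 80 for the same meal rises, so it would itself make AUC_P depend on fasting level. It would also leave Profile 3 at −28% and 128%.

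**Conclusion.** The concern holds as an internal inconsistency in SAP 5.11. When only AUC_B is negative, zeroing the areas overstates AUC_G by exactly 24 × (100 − F), which is 480 mg·h/dL at F = 80; this needs no assumption about profile shape. Zeroing only the percentages lets the shares leave the 0 to 100% range or reverse, and the sizes shown depend on the illustrative profiles and clock times. The number of affected subjects is unknown, and the range above rests on assumed means and SDs.

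The effect is confined to AUC_G, the shares, and their summaries, correlations and chart. It does not show bias between arms in AUC_P, and it leaves the primary and key secondary tests untouched.

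**What to change.** In SAP 5.11:

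1. Compute AUC_G directly as the trapezoid area under the 7-point curve, and state how the curve is closed from 0300 to 24 h.
2. Keep AUC_P as the net rise over fasting for the ANCOVA, and label it so. Keep AUC_B signed outside the share equations; the three parts then sum to AUC_G.
3. In the share equations only, replace AUC_B and AUC_P by max(AUC_B, 0) and max(AUC_P, 0). Treat the shares as undefined when both are zero, and report how many profiles that affects.

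Profiles 1 and 2 then give 100% postprandial, and Profile 3 gives 100% basal. Results for profiles with no negative component do not change. The cost is a few lines of SAP text and a short change to the derivation program. The possible downside is some loss of direct comparability with the cited publication.

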7.1.3. Blood Glucose Monitoring

The U-500R dosage will be based on subjects' individual needs, as assessed by SMBG results obtained from monitoring at home. Site personnel may request additional BG monitoring from subjects and/or assess BG values at other times during the study in order to make dose adjustment decisions. Subjects should record both 4- and 7-point SMBG measurements, as well as insulin doses, in the subject diary provided.

7.1.3.1. 4-Point SMBG

Subjects will be instructed to record 4-point SMBGs daily beginning with the screening period. The 4-point SMBG consists of BG measurements at:

- Pre-morning meal (fasting)
- Pre-midday meal
- Pre-evening meal
- Bedtime (at least 2 hours after the evening meal)

7.1.3.2. 7-Point SMBG

All subjects will be instructed to record 7-point SMBG profiles on any 2 nonconsecutive days in the 2 weeks prior to visits as outlined in the study schedule ([Attachment 1](#)); profiles should include weekend day(s), if possible. The timing of the 7-point SMBG measurement over a 24-hour period is as follows:

- Pre-morning meal (fasting)
- 2 hours after the morning meal
- Pre-midday meal
- 2 hours after the midday meal
- Pre-evening meal
- 2 hours after the evening meal
- 0300 hours

7.1.3.3. 0300 Hours SMBG

Subjects will also be instructed to record their 0300 hours BG within 48 hours of each increase in insulin dose titration at telephone and office visits (preferably the first night after the dosage adjustment). The investigator or site personnel will ask the subjects about these BG measurements and the **investigator** will recommend dosage titrations based on glucose targets within the CSII (Section 9.8.1.1) and MDI (Section 9.8.2.1) algorithms during telephone and office visits.

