- e Hypoglycemic and AEs should be collected in the subject’s diary and will be discussed during telephone visits and at the next onsite visit for each subject unless a severe hypoglycemic event occurs (SAE that needs to be reported immediately).
- f Subjects will be instructed to record 7-point SMBG profiles on 2 nonconsecutive days (including a weekend day if possible) in the 2 weeks prior to Visits 4, 13, and 17.
- g Health outcomes questionnaires will be administered prior to randomization during this office visit.
- h OmniPod U-500 System Exit Questionnaire will be administered to CSII subjects at ET if subjects terminate during treatment period.
- i Subjects will be introduced to the basics of the OmniPod U-500 system at investigator site before beginning CSII treatment but will not be given the device.
- j Subjects will receive hands-on training of the OmniPod U-500 system at investigator site using study drug and will be given device to begin CSII treatment.
- k Study drug assessed and dispensed based on need and expiration.

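### In SAP 5.11 the basal and postprandial areas do not cover the same hours, and LOCF can pair HbA1c with a glucose profile from another visit

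*SAP*

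**What the plan says.** SAP 5.11 derives four areas from the seven-point profile.

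- AUC_N is 100 mg/dL over 24 h, given as 2,400 "mg/dL per hour of exposure".
- AUC_B lies between 100 mg/dL and "a line projected rightward for 24 hours from the fasting (before breakfast) glucose value in the profile".
- AUC_P is "the area above the line projected rightward from the fasting sample before breakfast and below the line connecting the 6 remaining points". Stretches where the curve dips under the fasting level count negatively: the SAP says "minus any area below the line projected from the basal value, if applicable".
- AUC_G is the sum of these three and is described as the whole area under the curve.

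The postprandial share is AUC_P/(AUC_B + AUC_P), and the section adds "Negative values were set to zero".

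Protocol 7.1.3.2 introduces the profile with "The timing of the 7-point SMBG measurement over a 24-hour period is as follows" and then lists seven samples. The first is fasting and the last is 0300.

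The planned analysis includes a "Pearson correlation (p-value) between HbA1c CFBL at Week 26 (LOCF) and each of CFBL of" the areas and the two contributions, also at Week 26 (LOCF). AUC_B and AUC_P are compared between arms by an ANCOVA with only baseline and treatment. The other SMBG measures in 5.11 get an MMRM that includes the stratification factors.

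In the Study Schedule (Protocol Attachment 1), profiles are recorded "in the 2 weeks prior to Visits 4, 13, and 17", that is Weeks 0, 14 and 26, and the early-termination column of that row is empty. HbA1c is marked at Visits 1, 4, 10, 13, 15 and 17 and at early termination, so after randomization at Weeks 8, 14, 20 and 26 and on leaving.

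**The concern.** **Time base.** A share is interpretable when its numerator and denominator cover the same hours. Here the basal part always has 24 hours. The postprandial part stops at 0300, or about 20 hours after a 0700 breakfast. Taken literally, a line through only the six later points also starts at the post-breakfast sample, which leaves about 18 hours. Two programmers could reasonably produce different values of AUC_P from this text. The share, the bar chart by HbA1c category and the arm comparison of AUC_P all depend on the choice. Overnight insulin delivery differs by arm: CSII has its own overnight basal rate (Protocol 9.8.1), while MDI has three injections (Protocol 9.8.2.1). The omitted overnight piece may therefore differ by arm as well.

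**Pairing.** HbA1c is drawn more often than profiles are recorded. If LOCF is applied to each variable separately, the last HbA1c and the last profile of a subject who leaves early can come from different weeks. The correlation is then partly between glycemia at two different times.

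**Working it through.** **The plan's own figure.** 100 × 24 = 2,400 reproduces. The product is in mg·h/dL, so the printed unit is a slip.

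**Omitted areas.** Let F be fasting glucose, G2 the post-breakfast value and G3 the 0300 value. If the curve returns to F at 24 h, the trapezoidal rule gives:

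- closing piece, 0300 to next morning: gap × (G3 − F)/2. With breakfast at 0700 the gap is 4 h, so the piece is 2 × (G3 − F);
- first piece, omitted only under the literal six-point reading: 2 × (G2 − F)/2 = G2 − F.

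Because 5.11 subtracts area below the fasting line, the closing piece is negative when 0300 is below fasting.

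**Illustration.** These inputs are assumed, not taken from the documents: samples at 0700, 0900, 1200, 1400, 1800, 2000 and 0300, with values 150/210/170/200/165/205 and then G3. AUC_B = (150 − 100) × 24 = 1,200. With G3 = 160 the segments above fasting are 60 + 120 + 70 + 130 + 70 + 227.5 = 677.5, and the closing piece is 2 × 10 = 20. Only the last observed segment and the closing piece change with G3.

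| G3 | AUC_P to 0300 | Closing piece | AUC_P closed at 24 h | Share to 0300 | Share closed | Share, literal six points |
|---|---|---|---|---|---|---|
| 160 | 677.5 | +20 | 697.5 | 36.1% | 36.8% | 34.0% |
| 150 | 642.5 | 0 | 642.5 | 34.9% | 34.9% | 32.7% |
| 120 | 537.5 | −60 | 477.5 | 30.9% | 28.5% | 28.5% |

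The share is too low, unbiased or too high according to G3 − F. In the last row the two literal omissions (+60 and −60) cancel. AUC_P stays positive throughout, so setting negative values to zero does not act here.

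A second assumed profile has fasting 160, later values 215/180/215/185/220, and 0300 from 120 to 200. With breakfast between 0600 and 0900 (gap 3 to 6 h), closing the curve moves the share by −5.0 points (25.1% to 20.1%) up to +3.4 points (34.6% to 38.0%).

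The alternative common base cuts AUC_B to the observed 20 h. In the first profile AUC_B becomes 50 × 20 = 1,000 and the shares become 40.4%, 39.1% and 35.0%, all above the values to 0300.

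**Arm comparison.** With a 4 h gap, a 10 mg/dL arm difference in mean G3 − F shifts the AUC_P difference by 4 × 10/2 = 20 mg·h/dL. The documents give no such arm difference.

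**Pairing.** The inputs are 416 randomized (upper target, Groups A and B) and 25% dropout; an even spread of dropout over 26 weeks is an assumption.

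- Dropouts: 0.25 × 416 = 104, leaving 312 completers.
- Leaving after Week 14, so with a post-baseline profile: 104 × 12/26 = 48.
- Pairs available: 312 + 48 = 360. Mismatched at most: 48/360 = 13.3%.
- A subject leaving between Weeks 14 and 20 without an early-termination draw has both values from Week 14. With no such draws at all, only those leaving after Week 20 mismatch: 104 × 6/26 = 24, and 24/360 = 6.7%.

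**Effect on the correlation.** A simulation took N = 416, 25% random dropout, each dropout's last HbA1c at Week 8, 14 or 20 with equal chance, and a true Week 26 r of 0.40. All of these except N and the dropout rate are assumptions.

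- No time trend: LOCF r is 0.390 to 0.399 for visit-to-visit correlations of 0.5 to 0.9.
- Both measures still changing over time: LOCF r is 0.415 to 0.424, above the truth.
- Same trend, with visits matched but Week 14 pairs still carried forward: 0.438 to 0.440. Matching visits is therefore not enough; the pairs need to be observed at Week 26.
- Baseline profiles carried forward for early leavers: 0.374 to 0.382 without trend and 0.460 to 0.467 with it.

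A harsher check without trend halves r in all 13.3% of mismatched pairs: 0.867 × 0.40 + 0.133 × 0.20 = 0.373.

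**The case against.** Four points can fairly be made for the plan.

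1. *The literal six-point reading is strained.* SAP 5.11 says the areas come geometrically from the seven-point curve, which includes the fasting sample. This stands: the larger losses belong to the less likely reading. The wording still needs one clarifying sentence.
2. *Stopping at 0300 may be intended.* The section speaks of daytime glucose and of responses to the three meals. Adding nothing after 0300 is the same as holding glucose at the fasting line, so the areas can still be summed over 24 h. That is a possible convention, but it is not stated, and it makes the curve jump from the measured 0300 value to fasting. The section cites a published method; from the documents alone one cannot tell whether that source supplies a closing rule.
3. *Closing the curve at the fasting value is itself an assumption* that credits pre-dawn glucose to meals. This also stands, and it is why the same-hours alternative is offered.
4. *The consequences are small.* The objective is exploratory and outside H1 to H10, and 20 mg·h/dL is only about 3% of an AUC_P of 697.5. This stands.

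A reader might go further and infer that the postprandial share and its correlation with HbA1c must come out too low. The documents do not support that. Against a closed curve, the sign of the error follows 0300 minus fasting glucose, and the protocol anticipates both nocturnal hypoglycemia and a dawn phenomenon (9.8.1.2.1 and 9.8.1.2.2), so neither sign can be presumed. The share is low in every case worked only if AUC_B is shortened to the observed hours, a reference the SAP does not choose. For the correlation, a constant proportional understatement of AUC_P leaves Pearson's r unchanged, and LOCF pairing can lower or raise it.

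**Conclusion.** The point holds as a defect of definition and pairing, without a fixed direction of bias. As written, the share sets a 24-hour basal area against a postprandial curve that has no defined segment after 0300, and AUC_G equals the full 24-hour area only under an unstated convention. Under the assumed profiles and breakfast times, the error in the share against a closed curve runs from about 3 points too low to 5 points too high. An arm effect is possible, but the documents give nothing to size it.

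The LOCF mismatch affects a minority of pairs: roughly 7% to 13% under evenly spread dropout, and fewer if subjects who stop treatment stay in the study and record a Week 26 profile. With early leavers' baseline profiles not carried forward, r moved by about 0.01 to 0.03 in the cases tried, in either direction. Meal times, glucose values, dropout timing, the true r, visit-to-visit correlations and trends are all assumptions. No primary or key secondary conclusion depends on this analysis.

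**What to change.** In SAP 5.11:

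- State that AUC_P is computed by the trapezoidal rule on all seven points starting at the fasting sample, and that the curve is closed at 24 h with the fasting value. Alternatively, compute every area, including AUC_N and AUC_B, over the same observed hours. Correct the unit of AUC_N to mg·h/dL.
- Base the correlations on subjects with both HbA1c and a profile observed at Week 26, and keep the LOCF version as a sensitivity analysis.
- Compare AUC_B and AUC_P between arms with the MMRM, including stratification factors, that the section already uses for the other SMBG measures. The Week 14 and Week 26 profiles supply the repeated values.

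The cost is a few sentences and a small programming change. Subjects without a Week 26 profile leave the main correlation, which then describes those who reach that visit; the LOCF sensitivity analysis shows how much this matters. Closing the curve adds one assumed value per profile, which should be stated.
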